9.1.1.2. Time zero or baseline

Time zero (baseline) will be defined as the time at which the exposure status is assigned, when inclusion and exclusion criteria are applied and when study outcomes start to be counted,¹⁷⁻²⁰ and will be operationalised as follows:

- **Exposed group:** date of the first dose of bivalent BA.1 or bivalent BA.4-5.
- **Unexposed group:** calendar date on when they had not received any dose of the bivalent COVID-19 vaccine, matched to date of the first dose of bivalent BA.1 or bivalent BA.4-5 vaccine in the corresponding match. Time zero for an unexposed individual will be the same date as the corresponding date of the first dose of bivalent BA.1 or bivalent BA.4-5 in the exposed individual in the matched pairs.

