9.2.2. Exclusion criteria

Individuals who have had a diagnosis of the specific AESI being analysed within one year before time zero (to differentiate the recording of previous events from true new events) and at any time before time zero for diabetes type 1 will be excluded from the cohort and SCRI designs.

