Respiratory system	Acute respiratory distress syndrome	365	Cohort
Reproductive system	Secondary amenorrhea	183	Cohort
	Hypermenorrhea	183	Cohort
Skin and mucous membrane, bone and joints	Erythema multiforme	42	Cohort
	Chilblain-like lesions	42	Cohort
Other	Anosmia, ageusia	42	Cohort
	Anaphylaxis ^a	1 ³¹	Cohort/SCRI
	Multisystem inflammatory syndrome	42	Cohort
	Death (any causes)	365	Cohort
	Subacute thyroiditis	365	Cohort
	Sudden death	365	Cohort
Pregnancy outcome, maternal	Gestational diabetes	Any time pregnancy	Sub-cohort
	Preeclampsia	After 20 weeks gestation	Sub-cohort
	Maternal death	Any time pregnancy	Sub-cohort
Pregnancy outcome, neonates. Define design taking trimester into account	Foetal growth restriction	Any time pregnancy	Sub-cohort
	Spontaneous abortions	At spontaneous abortion	Sub-cohort
	Stillbirth	At birth	Sub-cohort
	Preterm birth	At preterm birth	Sub-cohort
	Major congenital anomalies ^a	1 year after birth	Sub-cohort
	Microcephaly	At birth	Sub-cohort
	Neonatal death	At birth	Sub-cohort
Termination of pregnancy for foetal anomaly	At termination	Sub-cohort	

090177e19fa902a7Approved\Approved On: 12-Jan-2024 21:20 (GMT)

Table 1. Safety outcomes: adverse events of special interest (AESIs) with estimated risk intervals and preferred study design

Body system / classification	Adverse event of special interest	Estimated risk interval (days)*	Preferred study design*
	Small size for gestational age	Any time pregnancy	Sub-cohort
Any	Severe COVID-19 ^b	Any	Cohort

SCRI = self-controlled risk interval

* Time zero corresponds to the day of vaccination (i.e., a 42-day risk interval means that individuals are followed from the day of vaccination to day 41). Risk interval based on the ACCESS project results and other publications.

a For these AESI clinical validation will occur.

b Severe COVID-19 defined as either COVID-19 hospitalisation or death

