9.7.1. Cohort design

9.7.1.1. Exposure assignment and follow-up

The main exposure of interest is in the receipt of at least one dose of the bivalent BA.1 or bivalent BA.4-5 vaccine. Individuals will be assigned to each vaccination category according to their data at time zero, as outlined below:

- **Exposed cohort:** Individuals will be assigned to this cohort when they receive a first dose of the bivalent BA.1 or bivalent BA.4-5 vaccine. Individuals will be censored if they receive a non-Pfizer COVID-19 vaccine during follow-up. For the matched comparative analyses individuals will be censored when their matched pair is censored.
- **Unexposed cohort:** Individuals will be assigned to this cohort if they have not received a COVID-19 vaccine at time zero. Individuals will be censored if and when

PFIZER CONFIDENTIAL

they receive a dose of any COVID-19 vaccine during follow-up. Time zero in the unexposed cohort will be the same day when they did not receive a Pfizer-BioNTech COVID-19 vaccine dose. This day will be chosen by calendar matching to the time zero of the corresponding exposed group.

Individuals will be followed from time zero (see [Section 9.1.1.4](#)) until the censoring described above, death, administrative end of follow-up, or end of study period 31 August 2024, whichever occurs first, with pregnancies followed until 30 June 2025 (see [Section 9.7.1.7](#)). For analyses of AESIs with known risk intervals, follow-up will be truncated at the end of the risk interval.

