9.7.1.4. Crude outcome measures

For safety outcomes with a known short risk interval ([Table 1](#)) (e.g., anaphylaxis), the risk (number of events/number of individuals in a cohort) and the corresponding 95% CIs will be computed. Effect estimates will be calculated both as risk differences and as risk ratios, with their corresponding 95% CIs, for those exposed to a Pfizer-BioNTech COVID-19 bivalent vaccine compared with the unexposed group that did not receive any COVID-19 vaccine during follow-up.

For safety outcomes with unknown risk intervals or those that require long follow-up (eg, death), the cumulative incidence will be computed, which will be estimated using the 1 – Kaplan-Meier estimator. Time to outcome will be defined as the time from the baseline date (time zero) until the occurrence of the outcome or censoring (Section 9.1.1.4 and Section 9.7.1.7). The variance will be computed using approaches that account for autocorrelation (eg, the robust estimator or via bootstrapping).^{39,40} Risk differences and risk ratios (and their corresponding 95% CIs) will be estimated at different time intervals, which will be adapted to the specific nature of each outcome.

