9.9. Limitations of the research methods

This study is subject to limitations related to both the study design and to the use of secondary health care data.

A data-related limitation of this study is the reliance on the accuracy of codes and algorithms to identify outcomes. Some outcomes and their dates of occurrence will be validated, but the extent of validation may be limited because of only partial access to medical records. It is

possible that some AESIs may be due to immunisation errors occurring during the administration of the bivalent BA.1 or bivalent BA.4-5 vaccines. This information is not regularly collected and it will not be possible to take these events into account with the current protocol. Exposure identification may be based on pharmacy dispensing records, general practice records, immunisation registers, medical records, or other secondary data sources. How specific COVID-19 vaccine products and dates of vaccination in these data sources will be identified is described in [Section 9.3.1](#). It is possible that vaccination of individuals outside the health care system will not be recorded in secondary EHR databases, thereby leading to potential bias because of exposure misclassification. Additionally, while every effort will be made to capture data on all variables, some data may not be identified or recorded in the data sources.

A study design-related limitation of both the cohort and SCRI designs is that any uncertainty regarding risk periods will lead to misclassification and underestimation of the risk. The estimation of cumulative incidence curves with a time zero starting on the date of the exposure assignment and eligibility assessment will minimise the impact of unknown risk periods, because there is an unvaccinated comparator and evaluation is done over the whole available follow-up.

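### Counting secondary amenorrhea from the vaccination day admits cases that began before time zero and dilutes the risk ratio

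*Protocol*

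**What the plan says.** Table 1 (Protocol 9.3.2) gives "Secondary amenorrhea" an interval of 183 days and the cohort design only. The row does not carry the mark for clinical validation. The table footnote sets the start for all rows: "a 42-day risk interval means that individuals are followed from the day of vaccination to day 41". By the same rule, 183 days means day 0 to day 182.

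Three other sections fix the counting:
- Section 9.1.1.2 defines time zero as the moment "when inclusion and exclusion criteria are applied and when study outcomes start to be counted".
- Section 9.7.1.1 cuts only the far end: "For analyses of AESIs with known risk intervals, follow-up will be truncated at the end of the risk interval". No later start is provided for any cohort outcome outside pregnancy.
- Section 9.2.2 removes prevalent cases through "Individuals who have had a diagnosis of the specific AESI being analysed within one year before time zero", so it acts on a record, not on onset.

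Section 9.9 acknowledges "reliance on the accuracy of codes and algorithms to identify outcomes". The protocol states no rule that dates an event back to its onset, and it neither defines secondary amenorrhea nor gives a delay from onset to diagnosis.

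**The concern.** Most outcomes in Table 1 can be recorded soon after they start. Secondary amenorrhea cannot, because menses must have been absent for some time before the diagnosis can be made. If that takes L days, a diagnosis recorded before day L belongs to an absence that began before vaccination (or before the matched date in the unexposed woman). Such a woman has no earlier diagnosis, so she passes the look-back and is counted as an incident case.

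Matching makes these cases about equally frequent in the two arms. They say nothing about the vaccine, but they enter the numerator and denominator of the risk ratio and move it toward 1. In a safety study that is the direction in which a real increase is understated. Nothing else planned for this outcome would reveal it: there is no self-controlled analysis, no clinical validation, and no sensitivity analysis in 9.7.1.11 that applies a lag.

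**Working it through.** **Inputs from the protocol.** Interval of 183 days starting on day 0 (Table 1 and footnote); 1:1 matching (9.1.1.3); precision scenarios in Table 3 (9.5).

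**Assumptions.** The lag L is not in the protocol; the range shown is 30 to 180 days. The background onset rate is constant, onsets before time zero are equal in both arms, and the true risk ratio is 2.

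**1. The plan's own figure.** Table 3, 100,000 per group, unvaccinated risk 1 per 5000, risk ratio 2: 40 against 20 events. SE of the log risk ratio = √(1/40 + 1/20 − 2/100,000) = 0.2738. The 95% CI is 2 × exp(±1.96 × 0.2738) = 1.17 to 3.42, as printed.

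**2. Dilution with a sustained effect.** In the unexposed arm, the share of the interval that can hold only onsets before time zero is L/183. Observed RR over days 0–182 = 1 + (RR − 1)(1 − L/183).

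| L (days) | L/183 | Observed RR, days 0–182 | RR, days L–182 |
|---|---|---|---|
| 30 | 16% | 1.84 | 2.00 |
| 60 | 33% | 1.67 | 2.00 |
| 90 | 49% | 1.51 | 2.00 |
| 120 | 66% | 1.34 | 2.00 |
| 180 | 98% | 1.02 | 2.00 |

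With RR = 1 the formula returns 1 for every L.

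**3. Effect limited to onsets on days 0–41, L = 90.** Affected diagnoses fall on days 90–131, which is 42 days.
- Days 0–182: 1 + 42/183 = 1.23.
- Days 90–272 (also 183 days): 1 + 42/183 = 1.23.
- Days 90–182 (93 days): 1 + 42/93 = 1.45.

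Moving the whole window later gains nothing here. Starting later and keeping the end does.

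**4. Precision and risk difference, Table 3 scenario, L = 90, sustained effect.**
- Days 0–182: 20 × 1.508 = 30.16 against 20 events. RR 1.51, SE 0.2883, CI 0.86 to 2.65. Excess 10.16 cases per 100,000.
- Days 90–182: 40 × 93/183 = 20.33 against 20 × 93/183 = 10.16 events. RR 2.00, SE = √(1/20.33 + 1/10.16 − 2/100,000) = 0.3841, CI 0.94 to 4.25. Excess again 10.16 cases per 100,000.

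The later start corrects the ratio and leaves the expected risk difference unchanged. The interval widens, but log RR divided by its SE rises from 1.43 to 1.80.

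**5. If diagnosis comes later than the definition allows.** With a 90-day definition and 30 further days of delay, counting from day 90 leaves 63 affected days of 93, so RR = 1 + 63/93 = 1.68, against 1.34 over days 0–182. A start at the minimum duration removes part of the dilution, so a range of L should be shown.

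**The case against.** The key number is not in the documents. They neither define the condition nor give a delay, and if codes are entered after roughly one missed period (L = 30) a true 2 still shows as 1.84. This stands: the direction follows from the nature of the condition, but the size is conditional on L.

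Event definitions and algorithms are to be built later (9.6), and detailed methods belong to the SAP, so the event could yet be dated to the last menses. That is possible and would be one of the two remedies. But the day-0 start is fixed in Table 1 itself, not deferred.

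The protocol partly anticipates the issue. Section 9.9 concedes that uncertain risk periods cause underestimation. Section 9.7.1.4 plans estimates at several time intervals, "which will be adapted to the specific nature of each outcome", for outcomes with unknown intervals or long follow-up. Yet there "Time to outcome will be defined as the time from the baseline date (time zero) until the occurrence of the outcome or censoring", so every such estimate is cumulative from day 0 and retains the early cases.

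A reader might also infer that causal cases are widely cut off at day 182. The documents do not support that as a general statement. With L = 90, days 0–182 capture every onset in the first 93 days, so loss at the end depends on how long an effect lasts. The 183-day length may already leave room for late diagnosis; the weak point is the start.

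**Conclusion.** The concern holds for the risk ratio. The day-0 start, with a look-back that acts only on recorded diagnoses, dilutes any true ratio other than 1: a sustained 2 becomes 1.84 to 1.34 for lags of 30 to 120 days and 1.02 at 180 days. This rests on an assumed lag, a constant onset rate and equal pre-vaccination onset in the two arms.

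Three stronger readings are not supported. The analysis is not driven to a null result whatever the truth, since intermediate lags leave a clear part of the effect and a true ratio of 1 is unbiased. The risk difference, which the protocol also reports, gains no expected spurious excess from these cases, only noise. Nor can one say that a detectable doubling is lost through the day-0 start alone: in the Table 3 scenario with L = 90, both the diluted interval (0.86 to 2.65) and the corrected one (0.94 to 4.25) include 1. The gain is an unbiased ratio and somewhat stronger evidence.

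The point deserves correction because the outcome is prespecified, the bias runs toward understating a harm, and the change is small.

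**What to change.** For secondary amenorrhea, in both arms, start counting at day L, where L is the minimum duration in the case definition (for example days 90–182 for a 3-month definition), among pairs still event-free and uncensored at day L. Alternatively, where the last menses is recorded, date the event to onset and exclude onsets before time zero.

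Report days 0 to L − 1 separately as a negative-control period, and show the risk ratio over a range of L. Treat an extension beyond day 182 (for example to day 272) as a sensitivity analysis for a sustained effect only, since it gains nothing over days 0–182 if the effect is confined to early onsets. The amendment log states that all vaccinees will have a year of follow-up by 31 August 2024, so the period is covered apart from censoring.

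The text change is one Table 1 entry, an exception in its footnote and a sentence in 9.7.1.1. The statistical cost is fewer events and a wider interval. The row would also differ from the monovalent vaccine PASS with which the outcomes are aligned, so the days 0–182 result should be reported alongside.

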9.3.3. Covariates

The following variables will be assessed at time zero (for the cohort design) or the date of initial vaccine dose (for the SCRI design) to characterise the populations, to define subgroups, or to control for confounding. Potential covariates may include the following information, as available in each data source:

9.3.3.1. Demographics

- Age:
 - Age will be grouped in categories in line with published background incidence rates from ACCESS (0-17, 18-29, 30-39, 40-49, 50-59, 60-65, 66-69, 70-79, 80+ years);
 - The age group 0-17 years will be stratified as follows, where feasible: 0-1, 2-4, 5-11, 12-15, 16-17;
- Sex;
- Pregnancy status and pregnancy trimester;
- Geographic region, as appropriate in each data source;
- Socioeconomic status (including housing, employment, and income, if available);
- Date of vaccination (categorised as appropriate, eg, by year or month).

9.3.3.2. COVID-19 history

- Previous diagnosis of COVID-19;
- Positive test result for COVID-19.

9.3.3.3. Personal lifestyle characteristics

- Smoking status;
- Body mass index.

9.3.3.4. Comorbidities

- History of anaphylaxis;
- History of allergies;
- Diabetes mellitus (types 1 and 2);
- Hypertension;
- Cardiovascular disease;
- Cerebrovascular disease;
- Chronic respiratory disease;
- Chronic kidney disease;
- Chronic liver disease;
- Cancer;
- Autoimmune disorders;
- Influenza infection or other respiratory infections;
- Charlson Comorbidity Index (CCI scales will be reported and additionally CCI component morbidities will be reported).
- CDC at risk groups

9.3.3.5. Immunocompromising conditions

- Immunodeficiencies;
- Immunosuppressant medication use;
- Human immunodeficiency virus and other immunosuppressing conditions.

9.3.3.6. Comedication use

- Comedication use during the year before time zero (prescriptions or dispensing, no over-the-counter medication use):
 - Analgesics;
 - Antibiotics;
 - Antiviral medications;
 - Corticosteroids;
 - Non-steroidal anti-inflammatory drugs;
 - Psychotropics;
 - Statins;
 - Novel oral anticoagulants;
 - Warfarin.

9.3.3.7. Healthcare utilisation

- Healthcare utilisation in the year and in the 2 weeks before time zero:
 - Number of hospitalisations;
 - Number of emergency department visits;
 - Primary care utilisation;
 - Cancer screening;
 - Other preventive health services, as appropriate
 - COVID-19 tests.

9.3.3.8. Other vaccinations

- Influenza;
- Pneumococcal;
- DTP (diphtheria, tetanus, and pertussis);
- TPV (polio);

- TV (MMR) (measles, mumps and rubella);
- Hib (Haemophilus influenzae type b);
- HB (hepatitis B virus);
- VV (varicella zoster virus);
- HZ (herpes-zoster virus);
- HPV (human papillomavirus);
- Meningococcal;
- Rotavirus.

9.3.3.9. Surrogates of frailty

The following variables will be used as surrogates of frailty (as available):

- Paralysis;
- Parkinson's disease;
- Skin ulcer;
- Weakness;
- Stroke/brain injury;
- Ambulance transport;
- Dementia;
- Difficulty walking;
- Psychiatric illness;
- Sepsis;
- Heart failure;
- Podiatric care;
- Bladder incontinence;
- Diabetes complications;

- Arthritis;
- Coagulation deficiencies;
- Vertigo;
- Lipid abnormalities.

The CDC at risk groups will be defined based on at-risk medical conditions for developing severe COVID-19 and will be reported as baseline characteristics for vaccinated and non-vaccinated individuals. These will be defined based on scientific evidence available on the US Centers for Disease Control and Prevention website and the UK National Health Services digital website. Those websites are updated regularly and provide a classification based on levels of evidence.

At-risk medical conditions that are considered as at higher risk to develop severe COVID-19 are summarised in [Table 2](#). Medicinal products that can be considered as proxies for these conditions are also listed. At-risk subgroups will be identified using medical codes and associated dates for at-risk medical conditions characterising at-risk groups for developing severe COVID-19 as well as prescription and/or dispensing records for drug exposures which may be used as proxies for their identification. At-risk subgroups will be created for each of the at-risk medical conditions listed in [Table 2](#). Multimorbidity, ie, individuals in more than one at-risk subgroup, will be included in each subgroup.

Table 2. Comorbidities and related medicinal products with evidence of being at high risk for developing severe COVID-19

At-risk medical conditions identified by diagnosis codes	Medicinal product proxy(ies) (ATC code)
Cancer (with chemo/immuno/radiotherapy, cancer treatment, immunosuppressant; targeted cancer treatment (such as protein kinase inhibitors or PARP inhibitors); blood or bone marrow cancer (such as leukaemia, lymphoma, myeloma))	Alkylating agents (L01A) Antimetabolites (L01B) Plant alkaloids and other natural products (L01C) Cytotoxic antibiotics and related substances (L01D) Other antineoplastic agents (L01X) Hormones and related agents (L02A) Hormone antagonists and related agents (L02B) Immunostimulants (L03) Immunosuppressants (L04)
Type 1& 2 Diabetes	Blood glucose lowering drugs A10A & A10B
Obesity (BMI > 30 kg/m ²)	Peripherally acting anti-obesity products (A08AB) Centrally acting anti-obesity products (A08AA)
Cardiovascular disease/ Serious heart conditions including heart failure, coronary artery disease, cardiomyopathies	Antiarrhythmics, class I and III (C01B) Cardiac stimulants excl. Cardiac glycosides (C01C) Vasodilators used in cardiac diseases (C01D) Other cardiac preparations (C01E) Antithrombotic agents (B01A)
Chronic lung disease including COPD, asthma, bronchiectasis, interstitial lung disease, cystic fibrosis, tuberculosis.	Drugs for obstructive airway diseases (R03) Lung surfactants (R07AA) Respiratory stimulants (R07AB)
Chronic kidney disease	Erythropoietin (B03XA01)
HIV	Protease inhibitors (J05AE) Combinations to treat HIV (J05AR) NRTI (J05AF) NNRTI (J05AG)
Immunosuppression	Immunosuppressants (L04A) Corticosteroids (H02)
Sickle cell disease	Hydroxyurea (L01XX05) Other haematologic agents (B06AX)
Hypertension	anti-hypertensive drugs (C02, C03, C07, C08, C09)

9.3.4. Data extraction

Each DAP will create ETL specifications using the standard ConcePTION ETL design template (accessible via this link:

<https://docs.google.com/document/d/1SWi31tnNJL7u5jJLbBHmoZa7AvfcVaqX7jiXgL9uAWg/edit>). Following completion of this template and review by study statisticians, each DAP will extract the relevant study data locally using their software (eg, Stata, SAS, R, Oracle). These data will be loaded into the CDM structure in comma-separated values (csv) format. These data will remain local (Figure 3).

090177e19fa902a7Approved\Approved On: 12-Jan-2024 21:20 (GMT)

9.3.5. Subgroups

Analyses in the matched cohort and in the SCRI study will be conducted in subgroups defined by baseline characteristics as follows:

- Pregnant women;
- Women of childbearing potential, defined as aged between 15 and 50 year old;
- Individuals who are immunocompromised;
- Individuals who have comorbidities;
- Individuals who have autoimmune or inflammatory disorders (eg, rheumatoid arthritis, inflammatory bowel disease);
- Prior influenza vaccination in the last 5 years (yes/no);
- COVID-19 primovaccination-defined subgroups:
 - Individuals who have not started primovaccination;
 - Individuals who have completed primovaccination with Pfizer's monovalent vaccine;
 - Individuals who have completed primovaccination with a Pfizer bivalent vaccine;
 - Individuals who have completed primovaccination with a non-Pfizer vaccine;
- COVID-19 booster-defined subgroups:
 - Individuals who have not received any booster;
 - Individuals whose last booster received was a Pfizer monovalent vaccine;
 - Individuals whose last booster received was a Pfizer bivalent vaccine;
 - Individuals whose last booster received was a non-Pfizer vaccine;
- Type of Pfizer bivalent vaccine received at baseline (bivalent BA.1 or bivalent BA.4-5).

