9.2.1.2. Self-controlled risk interval design

Individuals must meet all the following criteria to be eligible for inclusion in the SCRI design:

- have received a dose of Pfizer-BioNTech bivalent BA.1 or bivalent BA.4-5 vaccine;
- have not received any COVID-19 vaccine in the three months prior to the dose of bivalent BA.1 or bivalent BA.4-5;

PFIZER CONFIDENTIAL

CT24-WI-GL02-RF02 4.0 Non-Interventional Study Protocol Template For Secondary Data Collection Study

01-Jun-2022

Page 20 of 64

- have experienced the specific AESI during the risk or control interval;
- have full accrual of data used to define the event in both the risk and control interval combined, taking into account the data lag and timing of data extraction;
- have a minimum of 12 months continuous enrollment in the data source at time zero.

[figure not shown]

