9.7.2.2. Measures of association

Conditional Poisson regression will be used to estimate incidence rate ratios and their corresponding 95% CIs. AESI for which the SCRI design will be a secondary approach for AESIs, with their risk windows, are specified in [Table 1](#). The control period that will be the same length will follow the risk interval; more details will be provided in the SAP.

The SCRI inherently adjusts for both measured and unmeasured time constant factors such as sex and chronic health conditions with onset before the start of follow-up. Time-varying confounders may be included as covariates in regression models.

Analyses will be conducted in subgroups defined by demographic and clinical characteristics, dose number, and other covariates of interest when feasible.

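### The protocol does not separate same-day or recent non-COVID vaccination from past vaccination, which leaves the cohort and the SCRI open to the same co-administration bias

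*Protocol*

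**What the plan says.** Section 9.3.5 defines the subgroups for both designs. The only one that concerns a non-COVID vaccine is "Prior influenza vaccination in the last 5 years (yes/no". Section 9.3.3.8 names influenza, pneumococcal, zoster and other vaccines as covariates but gives no look-back period. The neighbouring covariates do have one: "Comedication use during the year before time zero" in 9.3.3.6 and "Healthcare utilisation in the year and in the 2 weeks before time zero" in 9.3.3.7. The lead-in to 9.3.3 says only this about timing: "The following variables will be assessed at time zero (for the cohort design) or the date of initial vaccine dose (for the SCRI design".

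Section 9.7.1.6 builds the cohort's inverse probability weights from the 9.3.3 covariates and leaves variable selection and weight construction to the SAP. The matching list in 9.1.1.3 contains no non-COVID vaccine. Neither do the eligibility rules (9.2.1, 9.2.2), the censoring rules (9.1.1.4, 9.7.1.8) or the sensitivity analyses (9.7.1.11).

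For the SCRI, the only vaccine restriction in 9.2.1.2 is that people "have not received any COVID-19 vaccine in the three months prior to the dose of bivalent BA.1 or bivalent BA.4-5". Section 9.7.2.2 states: "The control period that will be the same length will follow the risk interval". It allows, but does not require, time-varying confounders in the model, and it foresees further subgroups where feasible. It names no vaccine in either place. Section 9.9 presents the SCRI as the answer to residual confounding by factors that do not change over time, and it does not mention co-administration.

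**The concern.** The study period opens with the bivalent launch, in September 2022 at the earliest (9.2.3), when influenza vaccine may be offered at the same visit. The protocol does not say how often this happens. An exposed person's time zero is a vaccination visit. A control's time zero is that same calendar date, with no visit required (9.1.1.2). A same-day second vaccine is therefore likely to be far more frequent in the exposed.

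Table 1 gives many AESIs short windows counted from the day of vaccination: 1 day for anaphylaxis, and 42 days for Guillain-Barré syndrome, Bell's palsy, transverse myelitis and generalised convulsion. If a co-administered vaccine raises the risk of one of these, the cohort contrasts bivalent plus other vaccine with neither, and the SCRI risk interval contains both exposures. The SCRI is meant as a check on confounding in the cohort. For this source of bias it is not an independent check, so agreement between the designs would reassure more than it should.

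**Working it through.** **1. Does any provision separate same-day vaccination?**
- *Five-year subgroup.* If prior includes day 0, a same-day recipient shares a stratum with someone vaccinated four years ago. If it excludes day 0, a first-time same-day recipient falls in the no stratum. Neither reading isolates co-administration.
- *Cohort weights.* If the 9.3.3.8 covariate means history, co-administration is not adjusted for. If it includes same-day doses, adjustment rests on the few controls who have one. Illustration, assuming a same-day share of 0.50 in the exposed and 0.02 in controls, in equal groups: the propensity in that stratum is 0.50/0.52 = 0.96, so each such control has weight 0.52/0.02 = 26. Other controls have weight 1.48/0.98 = 1.51.
- *Seven-day health-care-contact sensitivity analysis.* It concerns contact before time zero, not a vaccine given at time zero.
- *SCRI.* A covariate fixed at the vaccination date is constant within a person and drops out of conditional Poisson regression. A same-day vaccine lies in the risk interval and never in the later control interval, so self-matching does not remove it. Only the optional time-varying terms could deal with later doses.

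**2. The plan's own figure.** The protocol has no figure on co-administration. Its only quantitative design element is Table 3. With a and b the expected events in exposed and unexposed, the limits are RR × exp(±1.96 × √(1/a − 1/n + 1/b − 1/n)). All 27 rows reproduce to rounding. For 1,000,000 per group, risk 1 per 50,000 and RR 2: b = 20, a = 40, SE = √(1/40 + 1/20) = 0.274, giving 1.17 to 3.42 as printed.

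**3. Size of a possible bias.** Let p1 and p0 be the shares with the other vaccine in exposed and controls (in the SCRI: in the risk and control windows). Let r be that vaccine's rate ratio for the AESI, and let the true bivalent RR be 1. Then

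observed RR = (1 + p1(r − 1)) / (1 + p0(r − 1)).

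All three inputs are assumptions; the protocol gives none of them.

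| p1 | p0 | r | observed RR |
|---|---|---|---|
| 0.3 | 0 | 1.5 | 1.15 |
| 0.5 | 0 | 2 | 1.50 |
| 0.6 | 0 | 3 | 2.20 |
| 0.3 | 0.02 | 1.5 | 1.15/1.01 = 1.14 |
| 0.1 | 0.3 | 3 | 1.2/1.6 = 0.75 |
| 0.7 | 0.3 | 3 | 2.4/1.6 = 1.50 |
| any | any | 1 | 1.00 |
| p1 = p0 | | any | 1.00 |

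Over p1 = 0.1 to 0.7 and r = 1.2 to 3, with p0 at 0 to 0.02, the range is 1.02 to 2.40. With p0 = 0.3 it is 0.75 to 1.50.

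**4. Against the planned precision.** In the Table 3 scenario above, an observed RR of 2 has a lower limit of 1.17, so a spurious value of that size would read as a signal. A spurious 1.15 would not: b = 20, a = 23, SE = √(1/23 + 1/20) = 0.306, limits about 0.63 to 2.09.

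**5. Precision of a restricted analysis.** If half the pairs were excluded (assumption), n = 500,000, b = 10, a = 20 and SE = √(1/20 + 1/10) = 0.387. The interval widens from 1.17–3.42 to 0.94–4.27.

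**The case against.** A reader might infer that the undated covariate and the five-year subgroup are the only controls. They are not. Other vaccinations enter the cohort weights through 9.3.3, the SCRI may add time-varying confounders, and further SCRI subgroups are possible. A covariate's look-back window is also something a SAP commonly settles, and the SAP is not at hand. This stands, and it means that a missing window is not in itself an error. It does not change the subgroup definition, which the protocol itself fixes. Nor does it help the SCRI, where a baseline covariate has no effect and an option is not a commitment.

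A reader might also infer that the other vaccine's adverse events are in fact credited to the bivalent vaccine. The documents do not support that. It would need frequent co-administration, unequal between groups or windows, and a raised risk of the specific AESI from the other vaccine. The protocol gives no figure for any of these.

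Nor is the direction fixed. Controls share the calendar date, age band and place of residence, so recent influenza vaccination, as opposed to same-day, need not be rare among them. In the SCRI, a vaccine given weeks later can fall in the control interval. Either can pull the estimate downward.

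Finally, a remedy that excludes people for vaccines received after day 0 can create bias. Assume 30% would otherwise be vaccinated over 84 days at a constant hazard, and that an AESI prevents this. Control-interval cases are then retained less often than risk-interval cases by a factor of 0.7^0.5, and a null rate ratio becomes 0.7^(−0.5) = 1.20. This stands and shapes the fix.

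**Conclusion.** The point holds as a gap that the protocol should close. Followed as written, neither design is committed to separating same-day or recent non-COVID vaccination from past vaccination, and both are exposed to the same bias for AESIs with short risk intervals. The mechanism follows from the text. The size does not. A null RR would appear as about 1.15 to 2.2 only under assumed shares of 0.3 to 0.6, rate ratios of 1.5 to 3, and near-zero same-day vaccination in controls. It would be unbiased if the other vaccine carries no risk for that AESI, and it could be biased downward where recent vaccination is common in controls or in the control window. That co-administration is much commoner in the exposed is an inference from how time zero is set and from the autumn launch, not a figure in the protocol.

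**What to change.** 1. **9.3.3.8 and 9.3.5:** alongside the five-year item, add a category assessed at time zero: other vaccine on the same day, other vaccine within the preceding risk-interval length, or none.
2. **9.7.1.11:** for AESIs with a risk interval of 42 days or less, add a sensitivity analysis limited to pairs in which neither member has a non-COVID vaccine recorded on day 0 or in the preceding risk-interval length. Report the co-administered stratum separately, labelled as bivalent plus other vaccine.
3. **9.7.2.2:** repeat the SCRI without people who have another vaccine recorded on day 0 or in the preceding risk-interval length. Handle later non-COVID vaccines as a time-varying covariate; do not exclude people because of them.

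The main analyses stay as they are. The cost is protocol wording, one restricted re-run per design, and lower precision in those runs (the widening in step 5 of the working, if half are excluded). The variables are already listed, but 9.3.3 makes covariates subject to availability, so the restricted analyses depend on how completely each data source records other vaccines. That should be reported by source.
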